10. STATISTICAL CONSIDERATIONS

10.1. Objective of the study

This is a single-arm prospective multi-center clinical study to evaluate the safety, performance, durability of TIES® Port in patients who require permanent ileostomy as its

CLINICAL INVESTIGATION PLAN

primary objective, and assessment of impact on quality of life in the implanted patients as its secondary objective. Acceptability of the TIES® solution for patients will be part of assessment of performance.

For patients who require a permanent ileostomy, the current available alternatives for emptying of ileal contents are (1) attaching a stoma bag to the end-ileostomy; (2) surgery to create a pelvic pouch through an ileo-anal anastomosis; and (3) surgery to create a continent ileostomy. All of these procedures are associated with complications and failure rates.

The TIES® solution is intended as an alternative to stoma bags in patients requiring end-ileostomy so that the patient has control over emptying of intestinal wastes and to minimise the need to wear stoma bags for collection and emptying of intestinal wastes. This is achieved by putting a TIES® Lid on the TIES® Port to control emptying of intestinal waste through the Port, instead of letting the waste empty continuously into a stoma bag. In addition, the TIES® solution can also be an option for patients who cannot tolerate use of stoma bags due to complications, failed continent ileostomy or failed pelvic pouch.

10.2. Study design

This protocol plans for five interim data analyses during the course of this open study. The first two interim analyses are planned after collection of 8-week results from the first 5 and of 24-week results of the first 20 subjects, respectively, to review all available study data and to assess if there is a need to modify the study protocol including adjusting the collection of outcome measurements for performance assessment. The third, fourth and fifth interim analyses will be conducted when 50, 100 and 150 subjects, respectively, have completed 24 weeks follow-up in order to assess the primary and secondary 24-week safety and performance endpoints, make a preliminary assessment of the types of patient with high device acceptability, and consider whether some of the secondary study instruments (e.g. Quality of Life Questionnaires) can be dropped on the remaining patients to simplify follow-up and reduce burden on patients and clinical teams.

10.3. Study Population Definition

The study population is defined according to the Intent-to-Treat principle. All enrolled subjects will be taken into consideration in the reported results, without any planned exclusion.

10.4. Performance Evaluation

The subject is assumed to empty the “bowels” about 6 times per day. 6-months is chosen as the time point for primary endpoint assessment because the subject is expected to be familiar with the use of the TIES® Lid as well as study procedures at that time.

- By analysing the frequency of use of the TIES® Lid versus the use of stoma bags in individual subjects, this gives an assessment of the usefulness and acceptability of the TIES® solution.
- Leakage around the stoma between emptying is to be assessed. For a conventional end-ileostomy, the peristomal skin is often in contact with the intestinal contents and at least 30% of the patients reported skin problems based on the literature. For patients with pelvic pouch, perfect continence is achieved in less than 80% of patients.

Performance evaluation is based on subject's assessment of performance as recorded on the 3-day diary preceding each scheduled follow-up at 16, 24, 36 and 52 weeks after

CLINICAL INVESTIGATION PLAN

operation. Performance evaluation applies only among subjects with the TIES® Port *in situ*.

Among subjects with the TIES® Port *in situ*, performance will be assessed according to (a) the proportion of subjects who use the TIES® Lid for continence control; (b) the proportion of subjects experiencing visible leakages around the implant; and (c) subject's assessment on the ease of use of the TIES® Solution.

Primary endpoint is absence of visible leakage or fecal staining of clothing at 24 weeks after implantation of the TIES® Port.

The success criterion at 24 weeks requires at least 70% of subjects with the TIES® Port *in situ* having no visible leakage or staining of clothing adjacent to the implant between consecutive episodes of using the lid for continence control. Spillage that might occur at opening of the lid is not regarded as leakage.

Secondary endpoints are

- Absence of visible leakage or fecal staining of clothing at 16, 36 and 52 weeks.
- Proportion of implanted subjects using the TIES® Lid for continence control at 16, 24, 36 and 52 weeks.
- Subject's assessment on the ease of use of the TIES® Lid using a visual analog scale 16, 24, 36 and 52 weeks after implantation.
- Subject's preference for the TIES® solution assessed at 52 weeks.

The subject's assessment on the ease of use of the TIES® Lid will provide feedback to the manufacturer regarding future refinements of the TIES® solution. Information will be collected in the diary to understand patient's needs and the number of stoma bags used as described in section 10.

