4. STUDY OBJECTIVE AND ENDPOINTS

The primary objective is to evaluate the safety, performance and durability of the TIES® Port to 52 weeks in subjects after implantation. The secondary objective is to evaluate Quality of Life (QoL) in subjects implanted with the TIES® Port.

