5.3. Subject Accountability

5.3.1. Enrolled subjects

The point of enrolment is the time at which, following recruitment, a subject signs and dates the informed consent to agree to participate in the clinical investigation. Subject for whom consent was not obtained prior to participation in the study will not be considered enrolled. No data from subject who has not provided signed informed consent will be included in any analysis.

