10.5. Sample size

The purpose of the study is to assess the durability and performance of the TIES® Port over one year. The table below shows the power to demonstrate non-inferiority to within 10% of the target 24-week performance criterion of 70% of subjects with the device *in situ* experiencing no leakage (i.e. lower two-sided 95% confidence limit no less than 60%) according to the true proportion and number of assessable subjects.

True proportion experiencing no leakage at 24 weeks	200 subjects	180 subjects	160 subjects	140 subjects	120 subjects
70%	87%	83%	79%	73%	67%
71%	93%	90%	87%	82%	76%
72%	97%	95%	92%	89%	83%
73%	99%	98%	96%	93%	89%
74%	99%	99%	98%	97%	94%
75%	100%	100%	99%	98%	97%

CLINICAL INVESTIGATION PLAN

There will be sufficient power with the planned 200 subjects to demonstrate non-inferiority of the TIES® Port with respect to the primary performance criterion (efficacy when device used as intended), if at least 80% of subjects are evaluable at 24 weeks (i.e. with at least 160 subjects). If the true proportion of patients experiencing no leakage is higher than the expected minimum of 70% there will be sufficient power to demonstrate non-inferiority even with fewer than the expected proportion of evaluable subjects at 24 weeks.

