10.6. Durability Evaluation

Durability of use is evaluated by the cumulative proportion of subjects with the TIES® Port *in situ* at each of the following timepoints of 8, 16, 24, 36 and 52 weeks. These are secondary endpoints.

Durability will be computed by lifetable methods as the complement of the cumulative proportion of subjects in whom the TIES® Port has been removed or has spontaneously explanted, with subjects censored if they withdraw from the study with the device *in situ*, have insufficient follow-up time, or the device is removed for reasons unrelated to device performance.

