10.9. Statistical analysis

Statistical analyses will be done using SAS System®, Version 9.2 or further and a complete statistical analysis plan will be written before the conduct of analysis. All statistical analyses will be made on locked databases following data clarifications resolved due to Data Management process.

No replacement of missing data is planned in the statistical analysis.

No statistical testing will be conducted for any other parameters in the study and only descriptive analysis will be provided to fully describe the parameters recorded.

Continuous variables will be summarized using standard quantitative statistics: number of non-missing observations, mean, standard deviation, median, quartiles and range (minimum and maximum observed values). The number of missing observations will also be specified.

Categorical variables will be summarized using classical frequency statistics: number of non-missing observations and percentages by categories. Percentages will be calculated on the number of non-missing observations. The number of missing observations will also be specified.

Durability of use will be analysed using lifetable methods to allow for censoring due to subject withdrawal and device removals for reasons unrelated to device performance.

Two-sided 95% confidence intervals will be computed for all primary and secondary endpoints.

A statistical analysis plan will be written to describe all derived variables used in the reporting (especially for all parameters to be compared in time: EQ-5d and Montreux QoL questionnaire) and the statistical tables and listings to be generated.

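### Section 10.3 declares intent-to-treat without exclusions, but the primary leak-free proportion counts only in-situ subjects with a diary, and no planned analysis gives the share of treated subjects with a retained, leak-free Port

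*Combined protocol and SAP*

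**What the plan says.** Section 10.3 sets one population for the whole study, by intent-to-treat: "All enrolled subjects will be taken into consideration in the reported results, without any planned exclusion". Enrolment is at consent, before surgery. Section 5.3.1 says: "The point of enrolment is the time at which, following recruitment, a subject signs and dates the informed consent".

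Section 10.4 uses a narrower group for the primary endpoint: "Performance evaluation applies only among subjects with the TIES® Port" in situ. The data source is the three-day diary before the visit, and the 70% criterion is written on the in-situ group. Section 10.9 plans no replacement of missing data and adds: "Percentages will be calculated on the number of non-missing observations". It also says that the count of missing observations will be reported.

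Section 10.5 shows that the narrower group is intended. It refers to "the primary performance criterion (efficacy when device used as intended), if at least 80% of subjects are evaluable at 24 weeks".

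Other sections cover part of what the primary result leaves out:
- Durability (10.6) is a life table of Port removal, reported at 24 weeks among other times. It censors subjects who "have insufficient follow-up time, or the device is removed for reasons unrelated to device performance".
- Safety (10.7) reports displacement, revision and replacement among all implanted subjects.
- Lid use among implanted subjects is a secondary endpoint at 24 weeks (10.4).
- Quality of life (10.8) is assessed in subjects with the device in situ.

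A separate analysis plan is still to come (10.9): "a complete statistical analysis plan will be written before the conduct of analysis".

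**The concern.** Sections 10.3 and 10.4 cannot both describe the primary endpoint. A reader who takes 10.3 at its word would read the headline percentage as covering everyone enrolled. It leaves out failed implantations, Ports lost before week 24, withdrawals and missing diaries.

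This matters because the study is single-arm with a fixed criterion. A Port removed early for leakage or poor ingrowth leaves the denominator and does not count against the device in the primary result. Section 4 names durability beside performance: "The primary objective is to evaluate the safety, performance and durability of the TIES® Port to 52 weeks in subjects after implantation". The share of treated subjects who still have the Port and do not leak is therefore a natural question, and no planned table answers it.

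Two points of definition also affect who is counted:
- Leakage is judged between one use of the Lid and the next (10.4). Section 7.1.3.3 provides for pausing Lid use for some weeks when ingrowth is incomplete. An in-situ subject could have no Lid episodes in the 24-week diary, and the plan does not say how that subject is classed.
- Under 6.9 a second implant restarts the visit schedule, so that subject's 24-week diary follows the second Port. Section 10.4 does not say this. For revisions, the restart is left to the investigator.

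**Working it through.** **Inputs.** From 10.5: 200 planned subjects, a 70% target, a lower two-sided 95% limit of at least 60%, and a floor of 160 evaluable. The plan gives no 24-week retention or diary-completion rate. The following are therefore assumptions: 200 attempted implantations, 70% leak-free among those assessed, and the numbers assessed or missing shown below.

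**The plan's own power figures.** Power = Φ((p − 0.60)/√(p(1 − p)/n) − 1.96). With p = 0.70 and n = 160: √(0.21/160) = 0.0362, 0.10/0.0362 = 2.76, 2.76 − 1.96 = 0.80, and Φ(0.80) = 79%, as printed. The 70% row gives 87.0, 83.3, 78.8, 73.3 and 66.7% against the printed 87, 83, 79, 73 and 67%. All 30 cells agree within 0.5 points. The table is sound for the in-situ estimate.

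**Same data, two denominators** (exact Clopper-Pearson 95% intervals).

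180 assessed, 20 not:
- In situ: 126/180 = 70.0% (62.7 to 76.6).
- All 20 fail: 126/200 = 63.0% (55.9 to 69.7).
- Half fail, half are leak-free at 70%: (126 + 7)/200 = 66.5% (59.5 to 73.0).
- All 20 do as well as those assessed: (126 + 14)/200 = 70.0%.
- 10 of the 20 are unrelated removals left out and the other 10 fail: 126/190 = 66.3% (59.1 to 73.0).

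160 assessed, 40 not:
- In situ: 112/160 = 70.0%.
- All 40 fail: 112/200 = 56.0% (48.8 to 63.0). This worst case mixes removals, withdrawals and missing diaries.
- All 40 do as well as those assessed: (112 + 28)/200 = 70.0%.
- Formal upper bound, all 40 leak-free: 152/200 = 76.0%.

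A subject whose Port is gone cannot have a retained, leak-free Port. The 70% and 76% figures therefore apply only if the unassessed subjects still had the Port and their leakage status was merely unknown.

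**Missing diaries among in-situ subjects.** Take 119/170 = 70.0% observed and 10 without a diary, k of whom were leak-free. The in-situ rate is (119 + k)/180, from 119/180 = 66.1% to 129/180 = 71.7%.
- 70% point criterion: 125/180 = 69.4% misses and 126/180 = 70.0% meets it, so it is missed if k ≤ 6. This example puts the observed rate exactly on the threshold. A higher observed rate would leave room.
- 60% limit (Wald): 119/180 gives 59.2%, 120/180 gives 59.8% and 121/180 gives 60.4%, so it is missed only if k is 0 or 1. The binomial probability of k ≤ 1 is 0.0001 if these subjects are leak-free at 70%, 0.15 at 30% and 0.38 at 20%. The rate in subjects without a diary is unknown.

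**The case against.** The strongest reply is that nothing is hidden. The in-situ restriction appears in the synopsis and in sections 4.1 and 10.4, inside the success criterion itself, and 10.5 labels it as efficacy under intended use. A result reported as specified names its own denominator. This stands: the estimand is legitimate, and only 10.3 mislabels it.

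A second reply is that the losses are reported. Ports removed for leakage or poor ingrowth are performance-related, so the durability life table counts them as events. Only unrelated removals are censored. Replacement and Lid use are given among implanted subjects, although 10.4 also places Lid use among in-situ subjects. From the count of missing observations a reader could work out the best and worst cases for missing diaries. This too stands in part, but none of these measures combines retention with absence of leakage in the same subjects.

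A third reply is that the unwritten analysis plan may add such an analysis. It may, but nothing commits to it.

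A reader might go further and infer one of the following, which the documents do not support:
- That the primary result will be biased upward as a measure of leakage. This requires that subjects who lost the Port leaked more often, which is plausible but not shown.
- That the study is underpowered. The power table refers to assessable subjects and reproduces.
- That missing diaries cannot matter for the 60% limit. This holds only if subjects without a diary do about as well as the rest.

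**Conclusion.** The point holds. Section 10.3 is wrong for the primary endpoint. It also does not fit safety (implanted subjects) or quality of life (in-situ subjects). Followed as written, the plan drops Ports lost for leakage or poor ingrowth from the primary denominator under an intent-to-treat label, and plans no combined figure beside it.

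The size depends on retention and diary completion, which the plan does not state. Under the assumptions above, a headline of 70.0% corresponds to 63.0 to 70% of all attempted implantations with 180 assessed, and to 56.0 to 70% at the plan's floor of 160. The lower ends are worst cases and not forecasts. The upper ends assume that unassessed subjects do as well as the rest. The choice of in-situ primary endpoint, its threshold and the sample size are not in question. The change should be made, but it does not invalidate the design.

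**What to change.** 1. **Section 10.3.** Replace the blanket intent-to-treat statement with the actual denominator of each endpoint family: performance, durability, safety and quality of life. State that the primary result and the 10.5 power table refer to the in-situ, as-used estimate.
2. **Section 10.4.** Before further 24-week data are analysed, state how in-situ subjects with no Lid episodes in the 24-week diary are classed for the primary endpoint. Say that for second implants the primary 24-week diary is timed from the new implantation, as 6.9 implies. Section 10.2 plans looks at 24-week data from 20, 50, 100 and 150 subjects. The documents do not show whether any has taken place.
3. **Supplementary analysis.** Keep the primary endpoint, threshold and sample size. Pre-specify a composite, Port retained and leak-free at 24 weeks from first implantation, over all subjects with attempted implantation, with a 95% interval and no pass mark. Failed implantation, and loss or replacement of the first Port before 24 weeks, count as not achieved. Add a sensitivity version that leaves out removals unrelated to device performance, as durability does. Show unknown status as a range from all failures to all successes.
4. **Missing diaries.** For in-situ subjects without a 24-week diary, report the same range beside the observed-case primary result.

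**Cost.** Wording in 10.3 to 10.5 and a few extra tables, with no new visits: explanted and attempted-but-not-implanted subjects are already followed for six months (5.3.3, 5.3.4). Withdrawn subjects have no further follow-up (6.17.2), and some revised subjects may have a reset schedule, so part of the supplementary result will be a range. A less favourable percentage will stand beside the headline.

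### The success criterion (at least 70% leak-free) is not the rule that section 10.5 powers (lower 95% limit at least 60%), so the stated 79–87% power does not belong to it

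*Combined protocol and SAP*

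**What the plan says.** The success criterion appears in the same words in the synopsis (Performance Evaluation), 4.1 and 10.4: "The success criterion at 24 weeks requires at least 70% of subjects with the TIES® Port" in situ to have no visible leakage or staining at 24 weeks. None of the three places mentions a margin, a confidence limit or a test.

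Section 10.5 introduces another rule, found only there. Its table gives power for "non-inferiority to within 10% of the target 24-week performance criterion of 70" per cent, which it explains as "lower two-sided 95% confidence limit no less than 60" per cent. At a true rate of 70% the table shows 87, 83, 79, 73 and 67% power for 200, 180, 160, 140 and 120 assessable subjects. The text below the table concludes that 200 subjects suffice to show "non-inferiority of the TIES® Port with respect to the primary performance criterion (efficacy when device used as intended", provided at least 160 are evaluable.

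Section 10.9 adds: "Two-sided 95% confidence intervals will be computed for all primary and secondary endpoints". It names neither an interval method nor a limit that decides success, and it leaves detail to a statistical analysis plan still to be written.

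**The concern.** The primary endpoint carries one pass/fail decision, and the plan contains two rules for it. The natural reading of 10.4 is that the observed proportion must reach 70%. The rule in 10.5 is already met at an observed 67% with 200 subjects. A reader of 10.5 is told that the study is well powered for its primary criterion, but the power shown is for the more lenient rule.

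Two things are at stake. First, a result between the two thresholds would be a success under one section and a failure under the other. Second, the choice could be made with the data in view. The study is open, and 10.2 has the primary endpoint assessed when 50, 100 and 150 subjects have completed 24 weeks. No success decision is planned at those looks, but the leak-free rate will be known. Section 10.9 requires the analysis plan only before the analysis is conducted.

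**Working it through.** **Inputs.** Target 70%, margin 10 points (threshold 60%), two-sided 95% limit, true rates 70–75% and 120–200 assessable subjects, all from 10.5. Pass mark 70% from the synopsis, 4.1 and 10.4.

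**Step 1: reproduce the 10.5 table.** With *p* the true rate and *n* the number of assessable subjects, use the normal approximation

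power = Φ( (p − 0.60) / √(p(1 − p)/n) − 1.96 ).

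- p = 0.70, n = 200: standard error √(0.21/200) = 0.0324; 0.10/0.0324 = 3.086; Φ(1.126) = 87.0% (stated 87%).
- p = 0.70, n = 160: standard error 0.0362; 0.10/0.0362 = 2.760; Φ(0.800) = 78.8% (stated 79%).

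All 30 cells reproduce to rounding. The table is right for the 60%-limit rule.

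**Step 2: probability of meeting the criterion as written.** The exact binomial probability that the observed proportion is at least 70% is P(X ≥ 140 | 200, p) or P(X ≥ 112 | 160, p).

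| True rate | n = 200: as written | n = 200: 10.5 table | n = 160: as written | n = 160: 10.5 table |
|---|---|---|---|---|
| 70% | 53.5% | 87% | 53.9% | 79% |
| 72% | 76.2% | 97% | 74.5% | 92% |
| 75% | 95.5% | 100% | 93.7% | 99% |

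Solving for 80% power, the rule as written needs a true rate of 72.4% (n = 200) or 72.6% (n = 160).

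**Step 3: where the verdicts differ.** The smallest counts whose lower 95% limit is at least 60% are:

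- n = 200: 134 with Wald, Wilson or Clopper-Pearson limits (the Clopper-Pearson limit at 134 is 0.6002). The criterion as written needs 140, so 134–139 gives opposite verdicts.
- n = 160: 109 with Wilson or Clopper-Pearson, 108 with Wald. The criterion as written needs 112, so 109–111 (or 108–111) gives opposite verdicts.

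Probability that the two rules disagree:

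| True rate | n = 200 | n = 160 (Wilson or Clopper-Pearson) |
|---|---|---|
| 70% | 30.7% | 19.0% |
| 72% | 18.7% | 13.5% |
| 75% | 4.1% | 4.3% |

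With Wald limits the n = 160 figure at a true 70% is 24.4%.

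**Step 4: below the target.** At a true 65% with n = 200, the 60%-limit rule passes 30.4% of the time and the rule as written 7.8%. The choice of rule therefore also changes how often a device below target is declared successful.

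**The case against.** The best defence is that the two statements fit together: 70% is the target, and the 60% limit is the test of non-inferiority to it. Section 10.5 does use the word target, states its rule openly in brackets, and never says that its figures are the chance of observing 70% or more. On this reading nothing has been miscalculated. Moreover, any point-estimate threshold is met about half the time when the true rate equals the threshold, so 54% is close to automatic. Section 10.5 also describes the true rate as possibly "higher than the expected minimum of 70" per cent, and the disagreement fades quickly above that. Finally, the promised analysis plan could settle the rule, and 11.2 requires amendments to be justified.

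Much of this is fair. The table is sound for its own rule, the target-plus-margin reading is plausible, and the gap does depend on the true rate. But no section says that the 60% limit decides success, and three sections state a 70% requirement with no margin. The claim about 160 evaluable subjects also rests on the 70% row, where the gap is widest. A later analysis plan could choose the rule, but it would leave the protocol's power statement attached to a criterion it does not describe.

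The choice of interval is a separate matter, because the plan names none. With Wald limits, exact power at a true 70% is 84.2, 81.5, 78.3, 74.3 and 69.4% for 200 down to 120 subjects. That is close to the table, and above it at 140 and 120. The fall to 73% at 160 subjects applies to Clopper-Pearson or Wilson limits.

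**Conclusion.** The concern holds and must be fixed. The primary decision rule in the synopsis, 4.1 and 10.4 conflicts with the rule powered in 10.5, and the power claim is attached to the wrong one. At 10.5's own base rate of 70%, the shortfall is 87 − 53.5 = 33.5 percentage points with 200 subjects and 79 − 53.9 = 25.1 points with 160. At a true 75% it shrinks to about 5 points at either size. These figures assume independent subjects, a binomial outcome, and the natural reading of the 70% criterion as an observed proportion. If the sponsor meant the 60% limit to decide, the table is about right as a normal approximation, and the error lies in the three statements of the criterion.

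**What to change.** State one rule, in the same words, in the synopsis, 4.1, 10.4 and 10.5, and name it with its interval method in 10.9. Do this before any interim look at the primary endpoint.

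- **If the 60% limit is intended:** *Success: the lower limit of the two-sided 95% Clopper-Pearson interval for the 24-week leak-free proportion is at least 60%; 70% is the planning value.* Clopper-Pearson is a suggestion; another named method would serve with its own exact power. Reword the sentence that 160 evaluable subjects give sufficient power, since the figure at a true 70% becomes 73%.
- **If an observed 70% is intended:** say so, replace the table, and remove the non-inferiority wording from 10.5.

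Replacement figures (%), Clopper-Pearson 60%-limit rule / observed at least 70%:

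| True rate | 200 | 180 | 160 | 140 | 120 |
|---|---|---|---|---|---|
| 70% | 84.2 / 53.5 | 76.9 / 53.7 | 72.9 / 53.9 | 68.1 / 54.2 | 62.2 / 54.5 |
| 71% | 90.6 / 65.5 | 85.0 / 65.1 | 81.4 / 64.7 | 76.8 / 64.2 | 71.0 / 63.8 |
| 72% | 94.9 / 76.2 | 90.9 / 75.4 | 88.0 / 74.5 | 84.1 / 73.5 | 78.8 / 72.5 |
| 73% | 97.5 / 85.0 | 95.0 / 83.9 | 92.8 / 82.8 | 89.8 / 81.5 | 85.3 / 80.2 |
| 74% | 98.9 / 91.3 | 97.5 / 90.3 | 96.1 / 89.2 | 93.8 / 87.9 | 90.3 / 86.4 |
| 75% | 99.6 / 95.5 | 98.8 / 94.7 | 98.0 / 93.7 | 96.6 / 92.6 | 94.0 / 91.3 |

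The cost is wording and one table. No extra patients are needed to make the text consistent. The downside is a less favourable power statement: at a true 70%, 84% instead of 87% (n = 200) and 73% instead of 79% (n = 160) with Clopper-Pearson, or about 54% with the observed 70% rule.

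### The 24-week success criterion judges leakage only between Lid episodes but divides by all subjects with the Port in situ, so read literally a subject who does not use the Lid counts as leak-free

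*Combined protocol and SAP*

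**What the plan says.** The criterion stands in the synopsis, section 4.1 and section 10.4 with the same wording: at least 70% of subjects with the Port in situ "having no visible leakage or staining of clothing adjacent to the implant between consecutive episodes of using the lid for continence control". Lid use is not a condition for entering the denominator.

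Other text describes the outcome differently:

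- Section 10.4, endpoint sentence: "Primary endpoint is absence of visible leakage or fecal staining of clothing at 24 weeks after implantation of the TIES® Port". It has no Lid condition.
- Section 10.4, measure (b): "the proportion of subjects experiencing visible leakages around the implant". It has no Lid condition either.
- Section 10.5 describes the criterion as "efficacy when device used as intended), if at least 80% of subjects are evaluable at 24 weeks", meaning at least 160 of 200. It does not define *evaluable*.
- Section 10.3: "All enrolled subjects will be taken into consideration in the reported results, without any planned exclusion".
- Section 10.9 bases categorical percentages on non-missing observations and plans no replacement of missing data. It does not say whether a non-user's outcome is missing. It also says that "a complete statistical analysis plan will be written before the conduct of analysis"; that plan is not among the supplied documents, and neither is the diary form.

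Non-use with the Port in place is foreseeable. A separate secondary endpoint is the "Proportion of implanted subjects using the TIES® Lid for continence control at 16, 24, 36 and 52 weeks". Section 6.9.2 makes starting the Lid depend on healing, and section 7.1.3.3 pauses it when ingrowth is incomplete.

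**The concern.** A subject who wears a bag throughout the three diary days has no interval between Lid episodes, and so no interval in which the criterion can record a leak. Taken literally, that subject adds one to both numerator and denominator. This coding can only raise the success rate, and it credits the device with continence where the Lid was not used. The other wordings lead to leaving the subject out, or to scoring any leakage around the implant directly.

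This is the only primary endpoint and the study is open. The third to fifth interim analyses are run "in order to assess the primary and secondary 24-week safety and performance endpoints". A rule chosen after those data are seen could be chosen, or be suspected of having been chosen, for its effect on the result.

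**Working it through.** **Inputs from the protocol.** Target 70% observed (10.4); lower two-sided 95% limit no less than 60% (10.5); 160 evaluable of 200 (10.5). **Assumption.** The documents give no non-use rate, so 5%, 10% and 20% of 160 in-situ subjects are shown (8, 16 and 32 non-users).

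**Step 1: reproduce the plan's power.** Power = Φ((p − 0.60)/√(p(1 − p)/n) − 1.96). For p = 0.70 and n = 160: √(0.21/160) = 0.0362; 0.10/0.0362 = 2.76; 2.76 − 1.96 = 0.80; Φ = 78.8% (plan: 79%). For n = 200, 180, 140 and 120 the formula gives 87.0, 83.3, 73.3 and 66.7% (plan: 87, 83, 73, 67%). The table is reproduced, so the same Wald limit, p̂ − 1.96√(p̂(1 − p̂)/n), is used below.

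**Step 2: where the two codings disagree on the 60% rule.** With 160 in the denominator the smallest passing count is 108 (67.5%, lower limit 60.2%). Counting u non-users as leak-free therefore needs only 108 − u leak-free users. Excluding them requires the users alone to pass. The chance of disagreement is the exact binomial probability that the number of leak-free users falls in the range.

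| Non-users (assumed) | Users | Leak-free users for which leak-free coding passes and exclusion fails | Chance if users truly 70% | Chance if users truly 75% |
|---|---|---|---|---|
| 8 (5%) | 152 | 100–102 (65.8–67.1%) | 13.1% | 1.3% |
| 16 (10%) | 144 | 92–97 (63.9–67.4%) | 22.4% | 2.3% |
| 32 (20%) | 128 | 76–87 (59.4–68.0%) | 33.5% | 4.4% |

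**Step 3: false-pass risk.** Let users be truly 60% leak-free, the bound to be excluded. With non-users counted as leak-free, the overall rate is 0.60(1 − u) + u, with u now the non-use share: 0.62, 0.64 and 0.68. The step 1 formula at n = 160 gives 7.5%, 18.3% and 58.3%, against 2.5% with no non-users. Exact binomial figures at 10% and 20% are 19.3% and 59.5%. With exclusion the chance stays near 2.5%.

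**Step 4: one data set.** Take 24 non-users (15%) and 88 of 136 users leak-free.

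- Counted as leak-free: (88 + 24)/160 = 112/160 = 70.0%, lower limit 62.9%. Both rules are met.
- Excluded: 88/136 = 64.7%, lower limit 56.7%. Both rules are missed.
- Leakage scored directly in non-users: 108 − 88 = 20 of the 24 must be leak-free to meet the 60% rule, and 112 − 88 = 24 of 24 to meet the 70% rule.

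**Step 5: where it does not matter.** With 16 non-users and 115/144 users leak-free, the results are 131/160 = 81.9% (limit 75.9%) and 115/144 = 79.9% (73.3%); both codings pass both rules. With 86/144, they are 102/160 = 63.8% (56.3%) and 59.7% (51.7%); both codings fail both.

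**The case against.** The strongest reply is that counting non-users as leak-free is the least natural reading. Section 10.4 speaks of assessing leakage between emptyings from diary records. Section 10.5 refers to efficacy with intended use in evaluable subjects, and section 10.9 uses non-missing denominators. Together these suggest that a subject with no Lid interval has no assessable outcome. The evidence for non-use at week 24 is also indirect: healing is judged at week 8, the pause lasts a few weeks and applies only to incomplete ingrowth, and week 24 was chosen because subjects should by then know the Lid. The pending SAP or the diary form may hold a rule, and no stopping rule or formal efficacy decision is attached to the later interim analyses.

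Much of this stands, and it lowers the severity. It does not remove the mismatch: the criterion as worded still divides by all in-situ subjects, and a SAP would have to choose between the protocol's own wordings.

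Two stronger readings are tempting and unsupported. A reader might infer that the plan has adopted leak-free coding; no passage states it, and it follows only from the literal wording. A reader might also infer from section 10.3 that non-users must count as failures. That section defines who enters the reported results, not how a subject is scored, and section 10.4 restricts performance to subjects with the Port in situ. Failure coding is a conservative sensitivity bound, so the sizes above compare leak-free coding with exclusion only.

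**Conclusion.** The point holds as a conditional one. The protocol's wordings of its primary outcome do not agree on an in-situ subject who does not use the Lid, and the literal wording favours success. Whether this changes the result depends on two unknowns: the share of non-users and the leak-free rate in users. The disagreement ranges on the 60% rule all lie below 70%, which section 10.5 treats as the expected minimum. At a true 75% the coding seldom matters for that rule, and with no non-use it never does. The more serious consequence is a false pass when users are near 60%. The 58% figure needs both 20% non-use and users exactly at that bound.

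This should be fixed, with medium confidence. The non-use rate is assumed, and a rule may exist in documents not supplied.

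**What to change.** Before the third interim analysis:

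1. Align the endpoint sentence, the success criterion and the meaning of *evaluable* in the synopsis, sections 4.1, 10.4 and 10.5, and the SAP, and reconcile them with section 10.3.
2. State that an in-situ subject with no Lid use in the 24-week diary is not counted as leak-free by default.
3. If efficacy with intended use is what is meant, make Lid use in the diary window the condition for *evaluable* and use that denominator. Acknowledge that this conditions on behaviour after implantation: if leaking subjects stop using the Lid, they leave the denominator and the rate rises.
4. For that reason, report the number of in-situ non-users with reasons, and a prespecified sensitivity analysis classing them as not successful.

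No change to the instruction on resting the Lid is proposed.

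The cost is text and one extra analysis. Section 10.4 already plans to analyse Lid against bag use in individual subjects, so no new data should be needed, although the diary form could not be checked. If non-users come out of the 160, power at a true 70% falls from 79% to about 74.5% (n = 144, 10% non-use) or 69.5% (n = 128, 20%). If the 20% allowance in section 10.5 already covers them, nothing is lost.
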